# LIST OF ABBREVIATIONS AND DEFINITIONS OF TERMS

AE Adverse event

ALT Alanine transaminase (SGPT)

ANOVA Analysis of variance

AP Alkaline phosphatase

AST Aspartate transaminase (SGOT)

AUC Area under the time-concentration curve

BSA Body surface area

BUN Blood urea nitrogen

CBC Complete blood count

CDER Center for Drug Evaluation and Research

 ${\rm C}_{\rm max}$  Maximum plasma drug concentration

Cmin Minimum plasma drug concentration

CFR Code of Federal Regulations

CI Confidence interval

CR Complete response

Cru Complete response / unconfirmed

CRF Case report form

CT Computed tomography

CV Coefficient of variation

CTCAE Common terminology criteria for adverse events

DLT Dose limiting toxicity

ECOG Eastern Cooperative Oncology Group

ECG Electrocardiogram

FDA Food and Drug Administration

GCP Good Clinical Practice

GGT Gamma glutamyl transferase

GLP Good Laboratory Practice

GMP Good Manufacturing Practice

Hct Hematocrit

HED Human equivalent dose

Hgb Hemoglobin

HGF Hepatocyte growth factor

HIPAA Health Information Portability and Accountability Act

IC50 Inhibitory concentration, 50%

ICH International Conference on Harmonisation

IEC Independent Ethics Committee

IND Investigational New Drug

IRB Institutional Review Board

LD Longest diameter

LDH Lactic dehydrogenase

MR Minor response

MRI Magnetic resonance imaging

MTD Maximum tolerated dose

NCI National Cancer Institute

NOAEL No observable adverse effect level

NOEL No observable effect level

ORR Overall response rate

PD Progressive disease

PK Pharmacokinetic

PR Partial response

qd Once daily

RECIST Response evaluation criteria in solid tumors

RP2D Recommended Phase 2 dose

RBC Red blood cell (count)

SAE Serious adverse event

sCR Stringent complete response

SD Stable disease

SE Standard error

SGOT Serum glutamic oxaloacetic transaminase (AST)

SGPT Serum glutamic pyruvic transaminase (ALT)

SPEP Serum protein electrophoresis

 $T_{max}$  Time to maximum plasma concentration

TNM Scale Tumor node metastases scale

ULN Upper limits of normal

UPEP Urine protein electrophoresis

VGPR Very good partial response

WBC White blood cell (count)

## 1 PRECLINICAL SUMMARY AND STUDY RATIONALE

# 1.1 Scientific Background of BBI608

Recent studies have uncovered the presence of cancer stem cells (CSC, also called tumor initiating cells or cancer stem-like cells) which have self-renewal capability and are considered to be fundamentally responsible for malignant growth, relapse and metastasis. Importantly, CSCs are inherently resistant to conventional therapies. Therefore, a targeted agent with activity against cancer stem cells holds a great promise for cancer patients (Lobo, Shimono et al. 2007 ; Boman and Wicha, 2008 ; Please find a list of updated reviews on cancer stem cells in all major cancer types in the special issue of *Journal of Clinical Oncology* on cancer stem cells (J Clin Oncol. 2008 Jun 10;26(17)). 

BBI608 is the most advanced product candidate selected from our BBI6000 program designed by Boston Biomedical, Inc. (BBI) to target cancer stem cells. BBI608 is a small molecule that targets cancer by blocking self-renewal of and inducing apoptosis in cancer stem cells. While not a kinase inhibitor, BBI608 works by inhibiting the CSCP3 pathway.

With our proprietary target discovery technology TPIV®, scientists at Boston Biomedical, Inc. have discovered that the CSCP3 pathway activity is critical for self-renewal and survival of cancer stem cells in human cancer. Blocking the CSCP3 pathway offers a novel and potentially highly effective strategy to target cancer stem cells as well as the bulk of the heterogeneous cancer cells, while sparing normal cells and normal adult stem cells

# 1.2 Preclinical Efficacy

Cancer stem cells are intrinsically resistant (more than 5 to 10 fold) to chemotherapeutic drugs. BBI608 has potent activity ( $\sim$ 100 to 500 nM) against cancer stem cells *in vitro* and *in vivo* while sparing normal hematopoietic stem cells (IC50 not reached at 30  $\mu$ M), offering a wide therapeutic window. The dependence on CSCP3 is conserved in various non-stem cancer cells. BBI608 has demonstrated *in vitro* efficacy in a broad spectrum of human cancer cell lines derived from both solid tumors and hematologic malignancies (IC50  $\sim$ 100 nM to 500 nM).

BBI608 monotherapy has demonstrated potent anti-tumor activity *in vivo* in multiple murine xenograft models of human cancer, including liver, head and neck, breast, prostate, colon, gastric and pancreatic cancers, in the absence of adverse effects. BBI608 monotherapy has demonstrated anti-metastatic activity using an *in vivo* spontaneous metastasis mouse models. These data suggest broad potential of BBI608 for a wide variety of human cancers.

# 1.3 GLP Toxicology

GLP 28-day repeat dose toxicology studies were performed in both rats and dogs at doses of 10, 30 and 100 mg/kg/day by oral gavage.

In the rat study, 100 mg/kg was not tolerated by the male rats. Toxic observations include significant weight loss, soft feces and diarrhea, and decreased food consumption, which led to early sacrifice. These observations recovered in the remaining male rats within 14 days after termination of dosing. Female rats receiving 100 mg/kg/day showed weight loss during the first week of dosing, however weight gain recovered during the continued dosing phase without significant abnormal clinical observations.

In the rat study, abnormal laboratory findings (azotemia, hyponatremia, hypochloremia, hyperkalemia, polycythemia, neutrophilia, monocytosis, and lymphopenia) were observed primarily in moribund male rats dosed at 100 mg/kg. These findings are consistent with acute renal failure in the setting of dehydration and diarrhea. In rats dosed at 100 mg/kg for 28 days, there was mild decrease in sodium, chloride and albumin levels and mild elevation of white blood cells, red blood cells, neutrophils, lymphocytes and monocytes. No significant abnormal laboratory findings in recovery rats, suggesting these abnormal laboratory findings are reversible. There were no abnormal laboratory findings in rats dosed at 10 and 30 mg/kg.

In the rat study, histopathological findings were noted in the rats dosed at 100 mg/kg, primarily in mordibund male rats, including microscopic changes in the stomach and urinary bladder (focal or multifocal chronic ulceration, epithelial hyperplasia, chronic active inflammation or hemorrhagic changes), in lymphoid tissues (mild to marked lymphoid atrophy with mild to moderate lymphocyte apoptosis in thymus; mild to moderate lymphoid atrophy and mild to moderate mastocytosis in mesenteric lymph nodes; mild to moderate lymphoid atrophy in 2 moribund male rats of the 100 mg/kg group and some elevation of hemosiderosis in the spleen) and in adrenal glands (mild cortical vacuolation). These findings are considered non-specific changes related to the test vehicle in the setting of dehydration and diarrhea. There were no significant histopathological findings in recovery rats, suggesting these histopathological changes are reversible. There was no significant test vehicle related microscopic changes in rats dosed at 30 mg/kg and 10 mg/kg.

In the rat study, toxicokinetics showed that all dose groups in rats achieved BBI608 exposure well above the predicted exposure levels needed for efficacy with exposure lasting beyond 10 hours.

For the dog study, toxicity was observed in dogs receiving 100 mg/kg/day consisting of mild weight loss, as well as clinical observations including emesis, diarrhea, mucoid and soft feces. These adverse effects were reversible within 14 days in the setting of continued dosing. No treatment related clinical pathology, gross pathology or histopathological effects were observed at any dose level. All dose groups achieved plasma levels of BBI608 above the predicted levels needed for efficacy, with exposure lasting beyond 10 hours.

The no observable adverse effect level (NOAEL, based on clinical observation, laboratory tests, gross and histopathological changes) for rats administered BBI608 daily orally over 28 days was 30 mg/kg/day (human equivalent dose: 180 mg/m²) and the NOAEL in dogs administered BBI608 daily orally over 28 days was 30 mg/kg/day (human equivalent dose: 600 mg/m²).

## 1.4 Safety and Encouraging Signs of Antitumor Activity in Phase I

A phase 1 dose escalation study (BBI608-101) in adult patients with advanced cancer was initiated to determine the safety, tolerability, recommended phase 2 dose (RP2D), pharmacokinetics and preliminary anti-tumor activity of BBI608. A modified Simon accelerated titration scheme was used for dose escalation, with a cycle consisting of twice-daily oral administration of BBI608 for 4 weeks, and was repeated every 4 weeks (28 days) until progression of disease, unacceptable toxicity, or other discontinuation criteria were met.

The dose of BBI608 has been escalated from 20 mg to 2000 mg/day, and a MTD was not reached. Further dose escalation is limited by pill burden. Adverse events have been generally mild; the most common being grade 1-2 diarrhea and nausea. Grade 3 events included fatigue and transient diarrhea. BBI608 has exhibited favorable pharmacokinetics. The plasma concentration of BBI608 reached several folds above the IC50. Prolonged stable disease beyond 12 weeks was observed in about 60% of evaluable patients, including patients with colon cancer, head and neck cancer, gastric cancer, ovarian cancer and breast cancer. Complete regression of a metastatic lesion to the kidney was also

observed in one colon cancer patient. Decrease in tumor markers (CEA and CA125) have been observed in colon cancer and ovarian cancer.

BBI608 has shown exciting signs of activity in colorectal cancer (CRC) patients in the phase I study where 22 CRC patients with k-Ras mutant or wild-type tumors have been enrolled. These patients were all end-stage patients who had failed standard treatments for CRC including FOLFOX, FOLFIRI, Avastin, EGFR therapy (if k-Ras wild-type) and experimental drugs. Thirteen (13) patients were evaluable with 8 (62%) showing SD or MR (27.6% regression) yielding a disease control rate (DCR=CR+PR+SD) of 62% compared to the historical control of about 10% for similar CRC patients on best supportive care. Progression free survival (PFS) was 13 weeks compared to the historical control of 7.7 weeks (hazard ratio = 0.382; 95% CI, 0.159 to 0.918; p=0.015) in CRC patients on best supportive care.

In addition, a phase Ib/II trial of BBI608 in combination with paclitaxel in patients with advanced malignancies carried out under IND 100,887 has shown that BBI608 given at 500 mg bid (1000 mg total daily dose) in combination with weekly paclitaxel is well tolerated.

In summary, BBI608 has shown an excellent safety profile, favorable pharmacokinetics, and encouraging signs of antitumor activity.

### 2 STUDY OBJECTIVES

# 2.1 Primary Objectives

The primary objectives of the study are:

• To assess the safety and preliminary anti-tumor activity of BBI608 in adult patients with advanced colorectal cancer who have failed first and second line treatment, when BBI608 is administered in combination with Cetuximab, or Panitumumab, or Capecitabine. The primary endpoint will be disease control rate, defined as the proportion of patients with a documented complete response, partial response and stable disease (CR + PR + SD) based on RECIST. The secondary endpoints will include progression-free survival (PFS) and overall survival (OS).

## 2.2 Secondary Objectives

The secondary objectives of the study are:

- To determine the pharmacokinetic profile of BBI608 and Cetuximab, or Panitumumab, or Capecitabine when administered in combination.
- To determine the pharmacodynamics (biomarkers) of BBI608.
- To evaluate tolerability of two dosing regimens of BBI608 by comparing administration of BBI608 at 240 mg twice daily starting dose and escalating to 480 mg twice daily after cycle 1 versus administration of BBI608 at 480 mg twice daily starting dose with dose adjustment permitted.
- To evaluate tolerability of BBI608 by comparing prophylactic administration of anti-diarrheal medication versus as needed administration of anti-diarrheal medication. The tolerability will be assessed using adverse event profile and achieved dose intensity.

## 3 SELECTION OF STUDY POPULATION

This study will be conducted in patients with advanced metastatic colorectal cancer.

The study may be conducted at sites in Canada, the United States, and Europe

# 3.1 Inclusion Criteria

Each patient must meet the following criteria to be enrolled in this study.

1. Signed written informed consent must be obtained and documented according to International Conference on Harmonization (ICH), Good Clinical Practice (GCP), the local regulatory

requirements, and permission to use private health information in accordance with the Health Insurance Portability and Accountability Act (HIPPA) prior to study-specific screening procedures.

- 2. A histologically or cytologically confirmed colorectal cancer that is metastatic, unresectable, or recurrent.
- 3. Patients must have received at least 2 regimens containing 5-FU, oxaliplatin, or irinotecan.
- 4. Patients to be enrolled in the Cetuximab or Panitumumab combination arms must have colorectal cancer which is K-Ras wild-type.
- 5.  $\geq$  18 years of age.
- 6. Measurable disease as defined by Response Evaluation Criteria in Solid Tumors (RECIST 1.1, see Section 9).
- 7. Karnofsky performance Status  $\geq$  70% (Section 15).
- 8. Male or female patients of child-producing potential must agree to use contraception or avoidance of pregnancy measures during the study and for 30 days after the last BBI608 dose.
- 9. Females of childbearing potential must have a negative serum pregnancy test.
- 10. Aspartate transaminase (AST) and alanine transaminase (ALT)  $\leq$ 2.5 × upper limit of normal (ULN), or  $\leq$  3.5 × ULN with metastatic liver disease.
- 11. Hemoglobin (Hgb)  $\geq$  10 g/dl.
- 12. Total bilirubin  $\leq 1.5 \times ULN$ .
- 13. Creatinine ≤ 1.5 × ULN or creatinine clearance > 60 mL/min/1.73 m² for patients with creatinine levels above institutional normal.
- 14. Absolute neutrophil count  $\geq 1.5 \times 10^9/L$ .
- 15. Platelets  $\geq 100 \times 10^9 / L$ .
- 16. Life expectancy  $\geq$  3 months.

## 3.2 Exclusion Criteria

Patients who meet any of the following criteria will be excluded from the study.

- 1. Anti-cancer chemotherapy, radiotherapy, immunotherapy, or investigational agents within 7 days of first dose provided all treatment-related adverse events have resolved or have been deemed irreversible, with the exception for a single dose radiation up to 8 Gray (equal to 800 RAD) with palliative intent for pain control up to 7 days before beginning the administration of BBI608.
- 2. Surgery within 4 weeks prior to first dose.
- 3. Any known symptomatic brain metastases requiring steroids. Patients with treated brain metastases must be stable for 4 weeks after completion of that treatment, with image documentation required. Patients must have no clinical symptoms from brain metastases and must be either off steroids or on a stable dose of steroids for at least 2 weeks prior to protocol enrollment. Patients with known leptomeningeal metastases are excluded, even if treated.
- 4. Pregnant or breastfeeding

- 5. Significant gastrointestinal disorder(s), in the opinion of the Principal Investigator, (e.g., Crohn's disease, ulcerative colitis, extensive gastric and small intestine resection)
- 6. Unable or unwilling to swallow BBI608 capsules daily.
- 7. Uncontrolled intercurrent illness including, but not limited to ongoing or active infection, clinically significant non-healing or healing wounds, symptomatic congestive heart failure, unstable angina pectoris, cardiac arrhythmia, significant pulmonary disease (shortness of breath at rest or mild exertion), uncontrolled infection or psychiatric illness/social situations that would limit compliance with study requirements.

### 3.3 Number of Patients

It is expected that approximately 60-80 patients will be enrolled in the study. Patient accrual will occur over a period of time dependent upon the number of cohorts enrolled.

### 4 INVESTIGATIONAL PLAN

# 4.1 Overall Study Design

This is an open-label, multicenter Phase II study of oral BBI608 administered with Cetuximab, or Panitumumab, or Capecitabine to patients with advanced metastatic colorectal cancer. The study is based on a Simon 2-stage design that will examine the safety, tolerability and pharmacokinetics of BBI608 and Cetuximab, or Panitumumab, or Capecitabine, and assess the preliminary anti-tumor activity of BBI608 when administered in combination with Cetuximab, or Panitumumab, or Capecitabine in patients with advanced colorectal cancer.

BBI608 treatment will be at a dose level of 480 mg twice daily (960 mg total daily dose). In each cycle, BBI608 will be taken daily continuously for 4 weeks (28 days). BBI608 will be administered twice daily approximately one hour prior to or two hours after meals with the first dose given in the morning and approximately 12 hours between doses.

For patients receiving Cetuximab therapy, Cetuximab will be administered IV on day 5 of cycle 1 at 400 mg/m² intravenous infusion over 120 minutes as the initial dose, then weekly at 250mg/m² over 60-minutes at subsequent cycles.

For patients receiving Panitumumab therapy, Panitumumab will be administered IV on day 8, and 22 of each 28 day cycle at 6 mg/kg over 60 minutes.

For patients receiving Capecitabine therapy, Capecitabine will be administered orally at 1000 mg/m^2 bid daily on days 8-21 every three weeks.

Cycles will be repeated until progression of disease, unacceptable toxicity, or another discontinuation criterion is met. In the case of toxicity, adjustment is permitted. If administration of Cetuximab, or Panitumumab, or Capecitabine is discontinued due to Cetuximab, or Panitumumab, or Capecitabine-related toxicity, administration of BBI608 will be continued until disease progression if tolerated.

Initially, 6 patients will be enrolled in each combination arm at a dose level of 480 mg twice daily (960 mg total daily dose) BBI608. If  $\leq 1$  out of 6 patients has an observable DLT in the combination regimen, then that arm of the study will continue to enroll patients at 480 mg po twice daily (960 mg total daily dose) of BBI608 following the Simon 2-stage design (see Table 1). If

DLT occurs in  $\geq 2$  of the 6 patients in a combination arm, then that arm of the study will be closed and no further patients will be enrolled. A given arm of the study of BBI608 in combination with Cetuximab, or Panitumumab, or Capecitabine will continue to enroll patients if no more than 1 out of 6 patients in the combination arm has an observable DLT.

Number of Subjects with DLT at 480 mg bid BBI608	DLT Decision Rule
≤ 1 out of 6	Continue patient enrollment in combination arm
≥2 out of 6	Close combination arm of the study

The following number of colorectal cancer patients will be enrolled based on a two-stage Simon design with an alpha of 5% and a power of 80% to detect a disease control rate improvement for Cetuximab and Panitumumab from about 30% (historical DCR for 3rd and 4th line colorectal cancer) to 60%, and a disease control rate improvement for Capecitabine from about 15% (historical DCR for 3rd line colorectal cancer) to 60%.

Table 1 Simon two-stage design for Phase II

	Patient number				
Combo Therapy	Stage 1	Stage 2	Total*		
Cetuximab	8	16	24		
Panitumumab	8	16	24		
Capecitabine	6	12	18		

\*If any of the three arms reach a DCR of 60% or more at the end of Simon Stage 2, a one-time option to expand accrual to a total sample size of up to 50 patients may be implemented for each arm.

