#### **Study Design:**

This is an open label, multi-center, Phase II study of BBI608 administered in combination with either Cetuximab, or Panitumumab, or Capecitabine. A cycle will consist of daily and continuous oral administration of BBI608 for four weeks in combination with either Cetuximab, or Panitumumab, or Capecitabine.

Arm A (Cetuximab) - BBI608 is administered at 480 mg po twice daily continuously and Cetuximab will be administered IV on day 5 at 400 mg/m² intravenous infusion over 120 minutes as the initial dose, then weekly at 250 mg/m² over 60-minutes at subsequent cycles.

Arm B (Panitumumab) - BBI608 is administered at 480 mg po twice daily continuously and Panitumumab will be administered IV on day 8 and 22 of each 28 day cycle at 6 mg/kg over 60 minutes.

Arm C (Capecitabine) - BBI608 is administered at 480 mg po twice daily continuously and Capecitabine will be administered orally at  $1000 \text{ mg/m}^2$  bid daily on days 8-21 every three weeks.

6 patients will be initially enrolled in each combination arm at a dose level of 480 mg twice daily (960 mg total daily dose) BBI608. If  $\leq 1$  out of 6 patients have an observable DLT in the combination regimen, then that combination arm may continue to accrue patients. If DLT occurs in  $\geq 2$  of the 6 patients in a combination arm, then the combination arm will closed and no new patients will be enrolled into this combination arm. A trial arm of BBI608 in combination with Cetuximab, or Panitumumab, or Capecitabine will continue to enroll patients only if no more than 1 out of 6 patients for each combination has an observable DLT. It is expected that approximately 60 to 80 CRC patients will be enrolled in the study.

Pharmacokinetics (PK) will be performed in the first cycle for the initial 6 patients of each combination arm of the study.

Pharmacodynamic assessments will be performed in patients with accessible tumors when tumor biopsy is possible.

Evaluation of anti-tumor activity of BBI608 in combination with Cetuximab, or Panitumumab or Capecitabine will be performed at about 8 week intervals while patients remain on study.

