Test Product, Dose, and Mode of Administration:	Patients in this trial will receive BBI608 orally at 480 mg twice daily (960 mg total daily dose). In each cycle BBI608 will be taken daily for 4 weeks (28 days). BBI608 will be administered twice daily, approximately one hour prior to or two hours after meals with the first dose given in the morning and doses separated by approximately 12 hours.			
	For patients receiving Cetuximab, Cetuximab will be administered IV on day 5 at 400 mg/m² intravenous infusion over 120 minutes as the initial dose, then weekly at 250mg/m² over 60-minutes at subsequent cycles.			
	For patients receiving Panitumumab, Panitumumab will be administered IV on days 8 and 22 of each 28 day cycle at 6 mg/kg over 60 minutes.			
	For patients receiving Capecitabine therapy, Capecitabine will be administered orally at 1000 mg/m  bid daily on days 8-21 every three weeks.			
	Cycles will be repeated until progression of disease, unacceptable toxicity, or another discontinuation criterion is met.			
Duration of Treatment:	continue radiologic most pati	dividual patient, treatment with BBI6 until unacceptable toxicity, discal) or another discontinuation crite ents will receive between one and period of 4 to 16 weeks.	ease progression (clinical or crion is met. It is expected that	

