## 5.3.1.4 Week 2 (Cycle 1, Day 12)

The following assessments will be made during this visit:

- Karnofsky performance status
- Vital signs (weight, pulse)
- Hematology (see Section 6.3)
- Blood chemistry (see Section 6.3)
- Liver function tests (see Section 6.3)
- Electrolytes (see Section 6.3)
- Assess AEs
- Record concomitant medication
- Cetuximab IV infusion, starting at about 3 hours after morning dose of BBI608 Dispense BBI608 (one week supply)

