## 7.1.3 Cetuximab, Panitumumab, or Capecitabine Administration

- Detailed instructions for the preparation, premedication, and administration of Cetuximab, Panitumumab, or Capecitabine are provided in the Product Labels approved by Health Canada or US FDA.
- Cetuximab will be administered via IV on Days 5, 12, 19 and 26 of a 28 day cycle, about 3 hours after the first daily dose of BBI608. Panitumumab will be administered via IV on Days 8, and 22 of a 28 day cycle, about 3 hours after the first daily dose of BBI608. Capecitabine will be administered orally twice-daily for two weeks out of three weeks. The first dose of Capecitabine should be taken about 3 hours after the first daily dose of BBI608 on day 8 of each 3 week cycle of Capecitabine.

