### Pharmacokinetic Sample Collection (Cetuximab Arm)

### Day 5-12 in CYCLE 1 ONLY

Cycle No.	Procedure	Sample No.	Desired Time
1	Draw blood sample	PK-01	-5 min
	Start BBI608 administration		0 min
	Draw blood sample	PK-02	30 min
	Draw blood sample	PK-03	60 min
	Draw blood sample	PK-04	120 min
	Draw blood sample	PK-05	175 min
	Start Cetuximab infusion		180 min
	Draw blood sample	PK-06	240 min
	Draw blood sample	PK-07	300 min
	Draw blood sample	PK-08	360 min
	Draw blood sample	PK-09	420 min
	Draw blood sample	PK-10	480 min
	Draw blood sample	PK-11	540 min
	Draw blood sample	PK-12	24 hour
	Draw blood sample	PK-13	27 hour
	Draw blood sample	PK-14	99 hour
	Draw blood sample	PK-15	171 hour

Day 26-33 in CYCLE 1 ONLY

Cycle No.	Procedure	Sample No.	Desired Time
1	Draw blood sample	PK-01	-5 min
	Start BBI608 administration		0 min
	Draw blood sample	PK-02	30 min
	Draw blood sample	PK-03	60 min
	Draw blood sample	PK-04	120 min
	Draw blood sample	PK-05	175 min
	Start Cetuximab infusion		180 min
	Draw blood sample	PK-06	240 min
	Draw blood sample	PK-07	300 min
	Draw blood sample	PK-08	360 min
	Draw blood sample	PK-09	420 min
	Draw blood sample	PK-10	480 min
	Draw blood sample	PK-11	540 min
	Draw blood sample	PK-12	24 hour

Draw blood sample	PK-13	27 hour
Draw blood sample	PK-14	99 hour
Draw blood sample	PK-15	171 hour

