- Intended DI (*dose unit/time unit*) = [intended cumulative dose per cycle] / [intended number of *time units* in a cycle]
- By cycle RDI (%) = $100 \times [by cycle actual DI] / [intended DI]$
- \circ Overall RDI (%) = 100 × [overall actual DI] / [intended DI]

Note the intended dose level is fixed at the start of treatment rather than the start of a cycle

- One exception is for Cetuximab. For Cetuximab, dose level is permitted to change from 400 mg/m^2 on day 5 in cycle 1 to 250 mg/m² for each subsequent infusion. If dose level decreases for Cetuximab 4-7 days after first dose date, then updated dose level is the new intended dose level for Cetuximab.
- Second exception is for all backbone therapies. All backbone therapies incorporate BSA or weight to calculate each dose. Panitumumab incorporates weight to calculate each dose-all other therapies incorporate BSA. Therefore, the BSA to be used for calculating each dose of the backbone therapies will be using the Mosteller method (see below) based on the last available weight and height prior to each infusion. For Panitumumab, the last available weight prior to each infusion will be used for calculating each dose.
- $BSA [m^2] = ((Height [cm] \times Weight [kg])/3600) \times 0.5$
- Calculated doses will be rounded to the nearest integer
- Cumulative dose, actual dose intensity and relative dose intensity will remain missing if they cannot be derived due to missing weight, or BSA. Height from the most recent earlier visit can be used if height is missing.

The intended cumulative dose of napabucasin per cycle is calculated by (intended dose level per day) \times (intended cycle duration in days)

• Intended dose level per day for napabucasin is 500mg po BID

Dose unit of napabucasin is mg, dose unit of other combination drugs (except Panitumumab) is mg/m^2 , dose unit of Panitumumab is mg/kg.

Treatment compliance

Treatment compliance for napabucasin is defined as follows:

(Cumulative actual total dose / total planned or intended dose) $\times 100 = \%$ compliance

For any IV combination drug (Cetuximab and Panitumumab), compliance will be calculated using the following equation:

(Number of treatments administered / number of treatments that should have been administered) $\times 100 = \%$ compliance

For oral combination drug (Capecitabine), compliance will be calculated using the following equation:

(Cumulative actual total dose / total planned or intended dose) \times 100 = % compliance

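### The protocol ties weekly cetuximab 250 mg/m² to later cycles but schedules three further infusions in cycle 1 with no dose or infusion time; the SAP starts 250 mg/m² at the second infusion

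*Protocol*

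**What the plan says.** Protocol 4.1 sets the first infusion: "Cetuximab will be administered IV on day 5 of cycle 1 at 400 mg/m² intravenous infusion over 120 minutes". It continues "as the initial dose, then weekly at 250mg/m² over 60-minutes at subsequent cycles". The synopsis has the same later-cycles wording under Study Design ("then weekly at 250 mg/m² over 60-minutes at subsequent cycles") and again under Test Product, Dose, and Mode of Administration. These are the protocol's three statements of the cetuximab regimen.

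The scheduling text is in other places. Section 7.1.3 says "Cetuximab will be administered via IV on Days 5, 12, 19 and 26 of a 28 day cycle", with no exception for cycle 1. The Day 12 visit of cycle 1 (5.3.1.4) lists "Cetuximab IV infusion, starting at about 3 hours after morning dose of BBI608", and the Day 19 and Day 26 visits (5.3.1.5, 5.3.1.6) list the same item. The Appendix D sampling table for Days 26-33 of cycle 1 has the line "Start Cetuximab infusion" at 180 minutes. None of these gives a dose or an infusion time.

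SAP 8.2.1, under extent of exposure, describes the cetuximab level as changing from 400 mg/m² "on day 5 in cycle 1 to 250 mg/m² for each subsequent infusion". It resets the intended level if the dose falls 4 to 7 days after the first dose date.

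**The concern.** A 28-day cycle holds four cetuximab infusions, so a change at the next cycle and a change at the next infusion are different instructions. The protocol's dose statements use the first, its schedule places infusions in the gap that this leaves, and the SAP uses the second. A site working from the protocol has no sentence that gives the dose or infusion time on Days 12, 19 and 26 of cycle 1.

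Those days fall in the first 28 days of BBI608 treatment. In that period, DLTs in the first six patients decide whether Arm A stays open. If sites resolved the wording differently, the six patients would not all have had the same cetuximab exposure. The cumulative dose, dose intensity (DI) and relative dose intensity (RDI) in the SAP also need an intended dose that the protocol does not state for those days.

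**Working it through.** The plan states no cycle 1 total for cetuximab, so there is no figure to reproduce. The check is a comparison of the passages, with simple arithmetic for illustration.

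**1. What each place fixes for Days 12, 19 and 26 of cycle 1**

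| Place | Infusion scheduled? | Dose or infusion time given? |
|---|---|---|
| Protocol 4.1 and synopsis (two places) | Not in terms; weekly dosing is attached to later cycles | 250 mg/m² over 60 minutes, attached to later cycles |
| Protocol 7.1.3 | Yes, all three days | No |
| Protocol 5.3.1.4 to 5.3.1.6 | Yes, one visit each | No |
| Protocol Appendix D, Days 26-33 | Yes, Day 26 | No |
| Protocol 7.2.1 rash table | Not addressed | Continue at 250 mg/m² after a first severe rash that improves; no cycle named |
| SAP 8.2.1 | Implied | 250 mg/m² from the second infusion |

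That the infusions take place is clear. No passage gives a second mg/m² figure for those days. What differs is the point at which weekly 250 mg/m² begins.

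**2. Intended cycle 1 total (illustration; neither figure is endorsed)**

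- Change at the second infusion, as the SAP words it: 400 + 3 × 250 = 1150 mg/m².
- Four infusions with 250 mg/m² starting only in cycle 2, assuming that the initial dose is repeated until then: 4 × 400 = 1600 mg/m². No passage states this assumption.
- Ratio: 1600 / 1150 = 1.39. A patient who received 1150 mg/m² has 100% of the intended dose on the first basis and 1150 / 1600 = 71.9% on the second. RDI equals these percentages only if the cycle has its intended length.

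**3. Position in the DLT window**

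DLTs are scored over the first 28 days of BBI608. Days 12, 19 and 26 are all inside, with Day 26 near the end.

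**4. The SAP's 4-to-7-day exception**

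- The SAP fixes the intended level at the start of treatment and updates it for cetuximab only if the decrease comes 4 to 7 days after the first dose date. I take that date to be the first cetuximab infusion.
- The planned gap is 12 − 5 = 7 days, the upper edge of the exception.
- Appendix A allows ±1 day. An infusion on Day 5 and the next on Day 13 are 8 days apart. With both visits shifted, the gap runs from 11 − 6 = 5 to 13 − 4 = 9 days.
- At 8 or 9 days the exception does not apply as written. The intended level stays at 400 mg/m², and each 250 mg/m² infusion counts as 250 / 400 = 62.5%.
- If the first dose date means the first BBI608 dose on Day 1, the gap to a nominal Day 12 is 12 − 1 = 11 days. Even a patient exactly on schedule would then fall outside.

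**The case against.** The strongest answer is that this is one loose phrase, in which cycles was written where infusions was meant. The SAP reads it that way, and the rash table in 7.2.1 treats 250 mg/m² as the standing dose with no cycle 1 exception. Section 7.1.3 also refers to the product labels for administration. All of that is fair, and the slip may be no more than wording. But the SAP does not govern dosing, the rash table covers only dosing after a severe rash, and the labels' text is not in the documents reviewed. A reference to a label does not remove three explicit sentences that do not fit the schedule.

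A reader might infer more: that the text allows anything from no further infusion in cycle 1 (400 mg/m² in total) to 400 mg/m² at every visit (1600 mg/m²), a fourfold range. The documents do not support that. Section 7.1.3, the three visit lists and the Day 26 sampling table rule out the no-infusion reading. Section 4.1 limits 400 mg/m² to Day 5 of cycle 1 and calls it the initial dose; no passage assigns it to a later day.

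The consequences can be overstated too:
- Events attributed to cetuximab are not DLTs, so the arm-closing rule is touched only through toxicity attributed to BBI608 or to the combination.
- The SAP plans PK parameters for napabucasin, capecitabine and 5-FU, not cetuximab, so the Day 26 profile adds little, although cetuximab PK is a secondary objective in protocol 2.2.
- Cetuximab compliance counts infusions, not mg.
- Nothing in the documents shows that sites read the text differently.

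**Conclusion.** The point holds as an inconsistency over when weekly 250 mg/m² dosing begins. It does not hold as a clash between two stated doses. The protocol's dose statements leave three scheduled infusions inside the DLT window without a dose or infusion time, and the SAP's starting point differs from the protocol's wording.

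On the SAP's wording the intended cycle 1 total is 1150 mg/m². The figure of 1600 mg/m², 39% higher, rests wholly on an assumption found nowhere in the documents and serves only as an outer illustration.

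The effect is limited to treatment consistency in Arm A, combination-related DLTs, and the cetuximab cumulative dose, DI and RDI. The DCR analysis and the sample size do not depend on it. The SAP's 4-to-7-day exception is a related, smaller defect: visits within the permitted window can fall outside it.

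**What to change.** Reconcile protocol 4.1 and both synopsis statements with 5.3.1.4 to 5.3.1.6, 7.1.3, the rash table in 7.2.1, the Appendix D sampling table and SAP 8.2.1. One statement should give the cetuximab dose and infusion time for each infusion day of cycle 1 and of later cycles, and the other places should refer to it. The sponsor must decide what it says; this review does not say which dose is right.

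In the SAP, define the first dose date used in the exception. Align the 4-to-7-day limit with the reconciled schedule and the ±1 day visit window, for example by tying the intended level to the infusion number instead of elapsed days. If dosing is already complete, the study report should state what was given on Days 12, 19 and 26 of cycle 1 and which intended dose the RDI uses.

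The cost is wording in the protocol and one derivation rule in the SAP. No new data, patients or analyses are needed.
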